**DO NOT DELETE ANY QUESTIONS FROM THIS TEMPLATE**

**PI Name:** [name]

**Study Title:** Development and pilot evaluation of a novel cooking skills intervention to prevent diabetes

**IRB No.:** IRB00018839

**PI Version No. / Date:** V2/ 01/05/2022

**I. Aims of the Study:** *Describe the aims/objectives of the research and/or the project's research questions or hypotheses.*

The Aim of this study is to **test the feasibility, acceptability, and preliminary effectiveness of the DPP Cooks compared with the standard DPP**. We will conduct a randomized pilot trial to test the feasibility and acceptability of DPP Cooks compared with the standard DPP among low-income adults. Data collection will occur at baseline, 4 months, and 12 months. The primary outcome is weight loss. Secondary outcomes include: dietary intake and quality; cooking confidence, attitudes, behaviors, and class attendance. Post intervention, I will also conduct focus groups with two groups: 1) with participants to understand their intervention experiences, and 2) with providers to examine program implementation and satisfaction.

**II. Background and Rationale:** *Explain why this study is being done. Summarize briefly what is already known about the issue and reference previously published research, if relevant.*

Incorporating targeted cooking skills interventions into behavioral weight loss programs to prevent type-2 diabetes, a growing public health problem that disproportionately impacts low-income populations, may be important to facilitate sustained dietary change, weight loss, and reduce risk of developing diabetes. The goal of this proposal is to create, and pilot test in a randomized pilot trial, a new cooking skills intervention to supplement the existing Diabetes Prevention Program while supporting the career development of a new investigator who aspires to a research career focused on preventing diet related diseases. Findings from this study will examine the importance of cooking skills for improving dietary intake, weight loss, and diabetes indicators, and will evaluate potentially important modifications to the DPP.

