The standard DPP group (control) will be offered a cooking skills session at the completion of the study as well as a participant workbook from the DPP Cooks.

All participants will have the following data collected:

Measure	Method	Baseline	4 months	12 months
Weight loss (kg and % of body weight)	In DPP meetings	X	X	X
Diet quality (3 days at each timepoint)	RFPM	X	X	
Cooking skills/ attitudes/ behaviors	Online Survey	X	X	X
Food Agency	Online Survey	X	X	X
Cooking confidence	Online Survey	X	X	X
Food security status	Online Survey	X	X	X
Demographics	Online Survey	X		
Acceptability of the DPP cooks	Interview			X
DPP session attendance	DPP Coaches			X

- ]
2. *Describe the number and type of study visits and/or contacts between the study team and the participant, how long they will last, and where/how they will take place.*

[ As described above, participants will participate in the DPP, which meets weekly for approximately 1 hour for six months, then approximately monthly for the last 6 months. Participants in the intervention arm (DPP Cooks) will have an additional 6 sessions in a teaching kitchen (2 hours each, 12 hours extra total). If the teaching kitchen is not open due to COVID-19 transmission rates, cooking classes will be held virtually over Zoom. If cooking sessions are virtual, study team staff will deliver the food and equipment needed to participant's homes. Study staff will maintain a safe distance when they deliver and will not enter participant's homes. Staff will drop off food and make sure it is received.

**We begin this study with virtual DPP Cooks classes. We will not begin in person classes at the teaching kitchen until we have been approved by the IRB to do so.**

The DPP Cooks arm will also be sent text messages during the latter 8 months of the intervention (after the 6 cooking sessions are complete) to act as cues to action to keep cooking and using the skills and recipes they developed.

Weight loss data will be collected per usual during DPP sessions by the coach. During virtual DPP, weight has been self-reported by the participant using DPP provided scales. Weight data is reviewed by the DPP team for quality and any issues are resolved with the participant. Weight data is collected in compliance with CMS standards. Weight data will be inputted by DPP staff into a spreadsheet saved on OneDrive. Participants will be identified by their study ID number only.

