Diet quality will be collected by the participant by taking photographs of all the food they eat over a 3-day period and uploading those photographs to the SmartIntake app. Participants will be reminded to do this based on text messages from the study team, and the study team will be on hand to assist participants if they run into any problems or need help. Participants will be given a reference card to include in food photographs (e.g. a blank white card with some lines on it to help gauge portion size as well as a paper food tracker and guidebook). Other measures of interest will be collected using online surveys (Qualtrics) at baseline, 4 months and 12 months. Finally, we will invite participants to share their thoughts and experiences with the DPP Cooks intervention in in-depth interviews (over Zoom or phone) at the end of the study (12 months).

]

- [ ]
3. *Describe the expected duration of the study from the perspective of the individual participant and duration overall.*

[The duration of the study is 12 months from start to finish. From the participant's perspective they will attend DPP sessions and some participants will have 6 extra cooking classes. Data collection will not require in person study visits. The participant will have a training session with study team staff to help them install and learn how to use the RFPM app and record their data. This session will take place over zoom before baseline data collection begins.

]

4. *Provide a brief data analysis plan and a description of variables to be derived.*

[The key independent variable for all analyses is an indicator of whether or not the participant is in the control (standard DPP) group or the intervention (DPP Cooks) group. The other key variable is an indicator of time (baseline, 4 months, or 12 months). The primary outcome variables are weight loss (in kg lost, and in % of body weight lost). The secondary outcome variable is dietary intake/quality. We will use the data from the RFPM to calculate Healthy Eating Index-2015 scores. We will also be able to measure fruit and vegetable, as well as carbohydrate intake. Additional secondary outcomes from survey measures will include cooking confidence, cooking attitudes, cooking behaviors, cooking skills, food agency, and food security status. For most analyses we will compare changes in scores from baseline to 4 months and baseline to 12 months between intervention and control groups.]

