- C. *Describe the anticipated frequency and severity of the harms associated with the risks identified above; for example, if you are performing "x" test/assessment, or dispensing "y" drug, how often do you expect an "anticipated" adverse reaction to occur in a study participant, and how severe do you expect that reaction to be?*

[ We do not anticipate any of the risks involved would be greater than those expected during daily life. ]

- D. *Describe the research burden for participants, including time, inconvenience, invasion of privacy in the home, out of pocket costs, etc.*

[ Participants will participate in the DPP (at least 16 weekly sessions of the first 6 months and at least 6 sessions in the last 6 months) and in the DPP Cooks arm will also participate in 6 2-hour cooking classes over the first 4 months. Participants will answer surveys at 3 time point, will complete 3 days of dietary recall (by taking pictures on their smart phone) at 2 time points, and will have the option to wear a CGM for 14 days at 2 time points. They will also have the option to participate in an in-depth interview after the completion of the program. In total, data collection activities should be a minor inconvenience and time commitment. Invasion of privacy is a very low risk and we do not anticipate any out of pocket costs. ]

- E. *Describe how participant privacy, and if relevant – family privacy - will be protected during data collection if sensitive questions are included in interviews, or if study visits occur in the home setting.*

[ Sensitive questions are not included in any data collection documents and there are no in person or in home data collection activities. ]

]

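### Acceptability against the standard DPP is an aim, but its only scheduled measure is an optional 12-month interview about DPP Cooks

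*Combined protocol and SAP*

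**What the plan says.** Section I (Aims) states that the trial will "test the feasibility and acceptability of DPP Cooks compared with the standard DPP among low-income adults". It adds: "Post intervention, I will also conduct focus groups with two groups". One group is participants, on their experiences; the other is "with providers to examine program implementation and satisfaction". Section I also lists class attendance among the secondary outcomes.

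The table in Section V.C.1 is introduced by "All participants will have the following data collected". It has one row on this subject, "Acceptability of the DPP cooks", collected by interview and marked at 12 months only. Its attendance row refers to DPP sessions.

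Two places make the interview voluntary. Section V.C.2 says "we will invite participants to share their thoughts and experiences with the DPP Cooks intervention in in-depth interviews (over Zoom or phone". The time it gives is month 12. Section VII.D says of participants: "They will also have the option to participate in an in-depth interview after the completion of the program".

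On exposure, Section V.C.1 places the six cooking classes in the first 4 months, and Section V.C.2 has text messages to the DPP Cooks arm for the remaining 8. The standard DPP arm "will be offered a cooking skills session at the completion of the study".

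Online surveys go to all participants at baseline, 4 and 12 months. Neither the table nor the analysis plan (Section V.C.4) lists an acceptability item among the survey measures.

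**The concern.** Section III.B justifies the sample size by the pilot's purpose: to learn how DPP Cooks can be implemented and to prepare a larger trial. Acceptability is therefore one of the main things this study should deliver, and the aim words it as a comparison.

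The scheduled measure does not match that aim in two respects. It concerns one arm's programme, so there is nothing to set beside it from the standard DPP. It is also taken only from people who choose to be interviewed, so it need not describe everyone assigned to DPP Cooks. Those who disliked the classes or stopped coming may be under-represented.

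Timing adds a smaller problem. Views on the classes, the main addition to the DPP in this arm, are sought well after the classes have finished, although a survey already goes out when they end. Attendance at those classes would be a useful objective companion measure, but the plan does not make clear that it will be recorded.

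**Working it through.** **1. The plan's own interval.** Inputs: classes in months 0 to 4 (Section V.C.1); interview at month 12 (table and Section V.C.2). Gap = 12 - 4 = 8 months. This reproduces the 8 months of text messages that Section V.C.2 places after the cooking sessions. The gap is longer for any cohort that finishes its six classes before month 4. It applies to the classes only; the text messages run to the end of the programme.

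**2. Scheduled acceptability measures, by arm and time.**

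- DPP Cooks: none at baseline, none at 4 months, one at 12 months (optional interview).
- Standard DPP: none at baseline, 4 or 12 months. The only row is about DPP Cooks, and this arm is offered a cooking session only once the study is over.

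A between-arm comparison needs at least one measure per arm. The schedule gives 1 against 0.

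**3. Who the interview describes.** At 48 participants randomised 1:1, each arm has 48 / 2 = 24. If *m* of the 24 opt in, the result describes *m*/24 of the arm and leaves (24 - *m*)/24 undescribed. The documents give no figure for *m* and no expected attrition, so neither fraction can be calculated, nor can any bias.

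**4. Interviews against focus groups.** Section I plans focus groups with participants and with providers, with no month given. The table and Sections V.C.2 and VII.D describe participant interviews only. No procedure describes a participant focus group or any contact with providers.

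**5. Attendance.** Section I names class attendance, and the table names attendance at DPP sessions. The recruitment text (Section V.A, DPP Screening) calls the weekly meetings classes, so the Section I term may mean DPP sessions, cooking classes or both. Section V.C.1 has coaches attending the cooking classes and research assistants on hand, so staff are available to keep a log. Its maximum size is 24 x 6 = 144 person-class entries.

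**The case against.** The strongest reply is that end-of-programme interviews are an ordinary and useful method in a pilot, and that month 12 is the end of the DPP Cooks package, text messages included. That stands. A reader might infer that the interview is simply mistimed; the documents do not support this. The 8-month gap concerns the classes only, and the interviews should be kept.

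Second, the phrase naming the standard DPP may only identify the trial's comparator. That is possible, but the sentence quoted from Section I mentions feasibility and acceptability alone, so a reader will take acceptability as something to be compared. If that is not meant, rewording the aim settles it.

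Third, the focus groups might fill the gap, and the survey might contain a satisfaction item. The questionnaires are not in the file, so an item cannot be ruled out, but neither the table nor the analysis plan lists one. The focus groups have no date or procedure. A reader might infer from Section VI.5, which names interview transcripts, that focus groups have been dropped. That does not follow, because the same sentence also covers other study data.

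Fourth, a reader might treat the table's all-participants heading as a promise of 48 interviews that other sections break. It is better read as a loose lead-in: the row label already limits it to DPP Cooks, and two other sections make the option plain. Aligning the wording is editorial.

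Finally, acceptability items put to one arm only, ahead of the self-reported cooking outcomes, could cue answers differently by arm. This is a fair warning and it shapes the fix.

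**Conclusion.** The point holds as a mismatch between a stated aim and its measurement. Followed as written, the plan yields views on DPP Cooks from those who opt in, collected about 8 months after the classes end. It yields no acceptability measure for the standard DPP arm. The comparison in Section I cannot then be made. This rests on the table and analysis plan being complete as to acceptability measures.

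Three stronger conclusions are not supported:

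- That the acceptability result will be biased by some stated amount. No uptake or attrition figure is given. One person is 1/24 = 4.2% of an arm, but this is true of any measure in an arm of that size and shows no bias.
- That response would be higher at 4 months. Section IX.B pays 60 dollars for 12-month data against 20 for 4-month data, which favours 12-month retention, though it does not say whether the interview counts. The gain at 4 months is shorter recall and a question put to everyone.
- That cooking-class attendance will go unrecorded. The term is undefined, which is a narrower fault.

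The primary weight outcome is unaffected. This is a worthwhile, inexpensive improvement to a pilot and does not threaten its main analysis.

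**What to change.** - **Survey.** Add a short closed-ended programme-acceptability scale to the existing 4-month Qualtrics survey in both arms. Place it after the cooking and food-agency items so that it does not cue those answers, and show the items on the cooking classes to the DPP Cooks arm only. Send it to everyone assigned, including those who stopped attending. Report the response rate and the result over all assigned.
- **Aim.** If no comparison is intended, restate the aim as acceptability of DPP Cooks.
- **Attendance.** Define class attendance. Have the coaches or study staff already present log each of the 6 cooking classes, in person or virtual, and report attendance over all assigned.
- **Interviews.** Keep them at 12 months and state that low attenders and early leavers will be invited.
- **Consistency.** Reconcile the focus groups in Section I with the interviews in Sections V.C.1, V.C.2 and VII.D: which will be held, with whom and when.

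The cost is a few extra minutes of participant time on a survey already being sent, and at most 144 log entries. People who have left may still not answer, which is why the response rate must be reported.

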**III. Study Design:**

A. *Provide a BRIEF overview of your study design and methods. The study design must relate to your stated aims/objectives. DETAILS WILL BE REQUESTED LATER. If your study also involves analysis of existing data, please complete Section XI, "Secondary Data Analysis of Existing Data" in the last part of this research plan. If your study ONLY involves analysis of existing data, please use the research plan template for secondary data analysis (JHSPH IRB Research Plan for Secondary Data Analysis of Existing Data/Specimens).*

This study is a randomized control pilot trial testing the DPP Cooks against standard DPP. DPP is a 12 month diabetes prevention behavioral weight loss program developed by the CDC and implemented

nation wide. Participants meet weekly for the first 6 month in group sessions, then meet less frequently over the last 6 months to help them maintain the behavioral changes (re: diet and physical activity) they made in the first six months. For this trial, up to 48 participants will be randomized 1:1 to participate in the 12 month DPP or the 12 month DPP *plus* an additional 6 cooking skills sessions (DPP Cooks) during the first 4 months of the DPP. The primary outcome, weightloss, is collected at weekly DPP sessions. The secondary outcomes will be collected via online surveys at baseline, 4 months and 12 months, and via the Remote Food Photography Method (RFPM) at baseline and 4 months.

- B. *Provide a sample size and a justification as to how you arrived at that number. If you use screening procedures to arrive at a final sample, distinguish the screening sample size from the enrolled sample size; a table may be helpful. For electronic survey studies involving online recruitment and survey completion: consider how you will set controls on how many people will join your study.*

The target sample size of 48 individuals, randomized 1:1 was based on the fact that this is a pilot feasibility trial so we are not necessarily concerned with detecting statistically significant results. Budget constraints preclude a higher sample size. This sample size will allow us to test the DPP Cooks with several cohorts to understand implementation and prepare for a larger, fully powered study in the future.

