**C. Study Implementation:**

1. *Describe the procedures that participants will undergo. If complex, insert a table below to help the reviewer navigate.*

All participants will receive the DPP intervention, a 12 month behavioral weight loss intervention developed by the CDC. The DPP is an evidence-based, standardized curriculum. It requires 1 year of program enrollment divided into two phases. In phase one, participants attend at least 16 1-hour weekly group sessions, and phase 2 includes at least 6 one-hour sessions during the last 6 months.

In the DPP, participants will have weekly group meetings with a trained coach and other participants (usually between 8-12 people in a cohort). Participants receive coaching and social support around topics such as nutrition and physical activity. Participants receive written materials to support their behavior change. They report current weight and minutes of physical activity at every DPP session which is recorded by the coach.

DPP sessions will take place virtually over Zoom.

In the DPP Cooks group, participants will also receive 6 additional 2-hour cooking skills classes throughout the first 4 months of the study period. The cooking classes will be taught by a professional chef-instructor at the *American Heart Association Simple Cooking with Heart Teaching Kitchen* located in the Under Armour House at [name] in Baltimore City. DPP Coaches will also attend the cooking classes. Research Assistants from the study team will also be on hand to assist and to help with clean up.

If the teaching kitchen is not open due to COVID-19 restrictions, cooking classes will also take place virtually over Zoom. The professional chef-instructor has experience leading virtual classes since classes pivoted to virtual in March 2020. If cooking sessions are virtual, we will deliver food and equipment needed for each session to the participant's home or arrange a pick up time for participants to pick up food at the teaching kitchen location (study staff will prepare bags of food for pick up and will be available at pre-arranged time for participants to come pick up). Study staff will not enter the home, but will deliver it to the participant's doorstep and will remain outside (and masked) to ensure it is received.

**We begin this study with virtual DPP Cooks classes. We will not begin in person classes at the teaching kitchen until we have been approved by the IRB to do so.**

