5. **Answer the following if they are relevant to your study design:**

- A. *If the study has different arms, explain the process for assigning participants (intervention/control, case/control), including the sequence and timing of the assignment.*

[DPP cohorts will be the unit of randomization to avoid cross over due to the group meeting format of the DPP. Randomization will occur the same way for everyone regardless of how they are recruited. We will run 2 DPP cohorts concurrently and one will be the intervention arm, and one will be the control arm. Participants will be assigned to the two study arms randomly. Once participants enroll in the study, they will be assigned to the 2 study arms using a random number function in Excel. Because the intervention requires a weekly DPP meeting, and this needs to fit in to the participant's life, we will create cohorts for randomization for whom 2 DPP meetings would be convenient. For example, if there is a DPP group on Thursday at 5:00 and another on Wednesday at 6:00 or 2 Thursday at 5:00 groups, we will create a spreadsheet of individuals for whom DPP meetings on Thursday at 5:00 or Wednesday at 6:00 will work. Then, we will use the random number function in Excel to assign those participants to 2 groups. We will also randomly determine which DPP cohort will be the intervention and which will be the control.]

- B. *If human biospecimens (blood, urine, saliva, etc.) will be collected, provide details about who will collect the specimen, the volume (ml) and frequency of collection, how the specimen will be used, stored, identified, and disposed of when the study is over. If specimens will be collected for use in future research (beyond this study), complete the "Biospecimen Repository" section below.*

[n/a ]

- C. *If genetic/genomic analyses are planned, address whether the data will be contributed to a GWAS or other large dataset. Address returning unanticipated incidental genetic findings to study participants.*

[n/a ]

D. If clinical or laboratory work will be performed at JHU/JHH, provide the JH Biosafety Registration Number.

[n/a ]

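### The plan compares changes from baseline without adjusting for baseline; adding each participant's own baseline score would modestly sharpen the diet and survey estimates at almost no cost

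*Combined protocol and SAP*

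**What the plan says.** The only analysis plan is section V.C.4 of the combined protocol and SAP. Its comparison is: "For most analyses we will compare changes in scores from baseline to 4 months and baseline to 12 months between intervention and control groups". The key independent variable is arm. The plan adds: "The other key variable is an indicator of time (baseline, 4 months, or 12 months", so baseline is one level of the time variable. No regression model is written out, and no baseline value or other covariate is named anywhere in the document.

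The baselines will exist. The data collection table in V.C.1 schedules cooking skills, attitudes and behaviors, food agency, cooking confidence and food security at baseline, 4 and 12 months. Its row "Diet quality (3 days at each timepoint" is marked at baseline and 4 months only. Section III.A agrees that diet is collected "via the Remote Food Photography Method (RFPM) at baseline and 4 months".

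Two features of the design bear on the size of the point. Section III.B sets the target at 48, randomized 1:1, because this is a pilot and the budget rules out more. Section V.C.1 describes DPP groups as "usually between 8-12 people in a cohort".

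**The concern.** Subtracting the baseline fixes its coefficient at 1. When baseline and follow-up are only moderately correlated, the best coefficient is smaller. The change score then over-corrects and carries extra baseline noise into the arm difference. Regressing on baseline estimates the coefficient instead.

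Preliminary effectiveness is one of the aims in section I, and the sample cannot grow. Using data already in hand is therefore one of the few inexpensive ways to narrow the secondary-outcome estimates. Three days of food photographs may correlate only loosely with three days taken 4 months later. If so, the diet score is where the change score loses most.

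**Working it through.** The plan has no figure to reproduce: III.B gives 48 without a power calculation, SD, correlation or dropout rate.

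**Inputs.** From the documents: N = 48, 1:1; cohorts of 8 to 12, so 48/12 = 4 to 48/8 = 6 cohorts, run as 2 to 3 concurrent pairs. Assumed: r from 0.3 to 0.9; ICC of 0, 0.05 or 0.10 on the residual; equal SDs at baseline and follow-up; baselines not clustered, because individuals are assigned at random within a pair.

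**Independent participants.** With outcome variance 1, the change-score contrast has variance proportional to 2(1 − r), and the adjusted contrast to 1 − r². The difference is 2(1 − r) − (1 − r²) = (1 − r)². That is the chance baseline imbalance left in by the change score. Removing it is the whole gain, not an extra benefit. Estimating the coefficient costs a factor of 1 + 1/(N − 4) = 1 + 1/44 = 1.023. So

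ratio = (1 + r)/2 × 1.023.

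**Clustered, with arm and cohort-pair terms.** With K cohorts of m = 48/K and DE = 1 + (m − 1) × ICC,

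ratio = (1 − r²)(DE + 1/(45 − K/2)) / [(1 − r)² + (1 − r²)DE].

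For K = 4, m = 12, ICC 0.05: DE = 1.55 and 1/(45 − 2) = 0.0233. At r = 0.5 this is 0.75 × 1.5733 / (0.25 + 0.75 × 1.55) = 1.180/1.4125 = 0.835.

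Variance ratio, adjusted to change score:

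| Setting | r = 0.3 | 0.5 | 0.7 | 0.9 |
|---|---|---|---|---|
| Independent | 0.665 | 0.767 | 0.869 | 0.972 |
| 4 cohorts, ICC 0.05 (DE 1.55) | 0.753 | 0.835 | 0.911 | 0.982 |
| 4 cohorts, ICC 0.10 (DE 2.10) | 0.805 | 0.873 | 0.933 | 0.986 |
| 6 cohorts, ICC 0.05 (DE 1.35) | 0.727 | 0.816 | 0.900 | 0.979 |
| 6 cohorts, ICC 0.10 (DE 1.70) | 0.770 | 0.848 | 0.919 | 0.984 |

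Simulation with 20,000 draws per setting agrees. For 4 cohorts and ICC 0.05 it gives 0.758, 0.837, 0.910 and 0.978. For independent participants it gives 0.672, 0.768 and 0.868 at the first three values of r, with 95% intervals covering 94.8% to 95.3%.

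**Interval width.** Narrowing is 1 − √ratio at equal degrees of freedom. For 4 cohorts and ICC 0.05 it is 13.2%, 8.6% and 4.5% at r = 0.3, 0.5 and 0.7.

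**Losses.** With 36 analysed (an assumed 25% loss) and independent participants, the cost factor is 1 + 1/32. The ratios are 0.670, 0.773, 0.877 and 0.980, so the picture hardly changes.

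**Weight.** If baseline weight and kg change correlate at 0, −0.15 or −0.3 (assumed), the ratio is (1 − ρ²)(1 + 1/44) = 1.023, 1.000 or 0.931. That runs from a 2% loss to a 7% gain.

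**Cohorts, for scale.** An analysis of cohort means with arm and pair terms leaves K − K/2 − 1 = 1 or 2 degrees of freedom. The 95% t multiplier is then 12.71 or 4.30, against about 2.02 at participant level.

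**The case against.** The case for leaving the plan alone is reasonable. The planned comparison is unbiased, the primary outcome gains little or nothing, and III.B says statistical significance is not the target. V.C.4 answers a form that asks for a brief plan. It speaks of most analyses and lists baseline as a time level, so an adjusted analysis is not ruled out. Every size above rests on an assumed r and ICC, and clustering can swamp it. At r = 0.5, ICC 0.05 and 4 cohorts, the half-width falls from about 0.69 to 0.63 SD with t = 2.02. With the cohort-level multiplier of 12.71 it falls only from about 4.4 to 4.0 SD, which is uninformative either way.

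Most of this stands, and it is why the point is modest. It does not remove the point, for three reasons:

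- A pilot that reports estimates still benefits from narrower intervals, and a gain remains in every clustered setting tabulated, though it is only 1% to 2% at r = 0.9.
- The time indicator does not settle the model. An arm-by-time model with unconstrained baselines and complete data returns exactly the change-score contrast, so adjustment has to be stated.
- Clustering is a separate gap that adjustment neither causes nor cures. In simulation at ICC 0.05 with 4 cohorts, intervals that ignored cohorts covered 84% to 90% for the change score and 83% to 88% after adjustment.

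One limit of scope also stands. Food security status may be categorical, and the format of the cooking behavior items is not given. The formulas apply to continuous scores only.

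**Conclusion.** The concern holds, as a worthwhile improvement and not a correction. For continuous diet and survey scores, adjusting for the participant's own baseline is better than the stated comparison of changes. Over r = 0.3 to 0.7 it cuts the variance by about 7% to 27% with ICC 0.05 to 0.10 and 4 to 6 cohorts, and by 13% to 33.5% with no clustering. Above r of about 0.9 the gain is negligible. For diet it applies at 4 months only, since there is no 12-month diet measurement. For weight no material gain is claimed. Confidence in the direction is high. Confidence in the size is moderate, because the documents supply neither correlation.

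**What to change.** In V.C.4, state that each continuous diet and survey score is analysed by regressing the change on arm and that participant's own baseline score. Using the follow-up value as the outcome gives the identical arm effect, and an equivalent baseline-adjusted repeated-measures model would also serve. Limit diet to 4 months, say which scales count as continuous, and leave weight as planned. Make the adjustment at participant level: with 4 cohorts, adding a cohort-mean baseline to arm and pair terms would leave no degrees of freedom. The cost is one sentence, one degree of freedom and about 2% of variance (1/44), already included in the figures above.

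Separately, settle the grouping. V.C.5.A says "DPP cohorts will be the unit of randomization to avoid cross over due to the group meeting format of the DPP", but also "Once participants enroll in the study, they will be assigned to the 2 study arms using a random number function in Excel" and "We will run 2 DPP cohorts concurrently and one will be the intervention arm, and one will be the control arm". State which describes the randomization (it may be meant as one sequence), include a term for the cohort pair, and say how grouping within cohorts is handled. With 4 to 6 cohorts the ICC cannot be estimated well, so show the interval for the arm effect over a stated range, for example 0 to 0.10. Intervals that allow for cohorts will be wide with or without baseline adjustment; that cost comes from the design.
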